Concomitant therapies for Crohn's disease including 5-ASAs, corticosteroids, antibiotics, and immunomodulators (ie, AZA, 6-MP, or MTX), and/or total parenteral or enteral nutrition may be administered and changed at the discretion of the investigator.

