From Week 12 through Week 48, participants may transiently use (ie, for <4 weeks) increased doses of corticosteroids for reasons other than treatment for Crohn's disease (eg, stress doses of corticosteroids for surgery, asthma, adrenocortical insufficiency).

After Week 48 and through Week 96, concomitant therapies for Crohn's disease including 5-ASAs, corticosteroids, antibiotics, and immunomodulators (ie, AZA, 6-MP, or MTX), and/or total parenteral or enteral nutrition may be administered and changed at the discretion of the investigator.

Participants who discontinue study intervention early should return for a study intervention discontinuation (SID) visit. All randomized participants should complete the FES follow-up visit approximately 12 weeks after the last dose of study intervention.

Randomization and Blinding

Randomization will be used to minimize bias in the assignment of participants to treatment groups, to increase the likelihood that known and unknown participant attributes (e.g., demographic and baseline characteristics) are evenly balanced across treatment groups, and to enhance the validity of statistical comparisons across treatment groups. Blinded treatment will be used to reduce potential bias during data collection and evaluation of clinical endpoints.

Central randomization will be implemented in this study. It is based on a computer-generated randomization schedule prepared before the study by or under the supervision of the sponsor. Allocation to treatment groups will be performed using an interactive web response system (IWRS). The IWRS will assign a unique treatment code, which will dictate the treatment assignment and matching study intervention kit(s) for the participant.

At Week 0, a target of 318 total participants will be randomly assigned in a 1:1:1 ratio to one of the treatment groups using a permuted block randomization. The randomization will be stratified by baseline Crohn's Disease Activity Index (CDAI) score (\leq 300 or >300), baseline Simple Endoscopic Score for Crohn's Disease (SES-CD) score (\leq 12 or >12), and prior BIO-Failure status (Yes or No).

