5.4.2. Estimands

5.4.2.1. Estimands for the Secondary Endpoints

Secondary Estimand of Clinical Remission at Week 24 (Main Estimand 5)

The following describes the attributes of the Main Estimand 5.

Treatment by Week 24:

Experimental:

- Guselkumab ^{CCI} q4w (Weeks 0, 4, and 8) followed by guselkumab ^{CCI} q4w (Weeks 12, 16, and 20)
- Guselkumab ^{CCI} q4w (Weeks 0, 4, and 8) followed by guselkumab ^{CCI} q8w starting at Week 16

Control: Placebo SC q4w (Weeks 0, 4, 8, 12, 16, and 20)

Population: Participants with moderately to severely active Crohn's disease

Variable (Endpoint):

A binary response variable (response/nonresponse) where response is defined as achieving CDAI score <150 at Week 24 without experiencing any of the ICEs in categories 1, 2, 3, 5 and 6 as outlined below prior to the Week 24 visit.

Intercurrent events and corresponding strategies:

ICE Identifier	ICE Description	Corresponding Strategy
1	A Crohn's disease-related surgery (with the exception of minor procedures such as drainage of a superficial abscess or seton placement, etc.)	Composite
2	A prohibited change in Crohn's disease medication (See Appendix 2)	Composite
3	Discontinuation of study intervention due to lack of efficacy or an AE of worsening of Crohn's Disease	Composite
4	Discontinuation of study intervention due to COVID-19 related reasons (excluding COVID-19 infection) or regional crisis	Treatment Policy
5	Discontinuation of study intervention due to COVID-19 infection or for reasons other than those specified in ICE categories 3 and 4	Composite
6	Meets rescue criteria as determined by the IWRS	Composite

The composite strategy assesses the treatment effects not only based on the variable measurements, but also based on ICEs. This estimand acknowledges that having an ICE in categories 1-3, 5 and 6 is an unfavorable outcome. For participants experiencing ICE category 4, the treatment policy strategy considers the occurrence of ICE category 4 is irrelevant in defining the treatment effect.

Population-level summary:

Difference in proportions of responders (according to the **Variable** defined above) between each guselkumab group and the placebo group.

Secondary Estimand of PRO-2 Remission at Week 12 (Main Estimand 6)

The same estimand (except for the "Variable" attribute) that is specified for the co-primary endpoint analyses will be used.

Variable (Endpoint):

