Similar methodology used for analyzing endpoints through Week 24 will be applied to the endpoints analyses after Week 24. Specifically, the estimand approach and analysis methods specified in Sections 5.4.2.1 and Section 5.4.3.1 for the secondary endpoints will apply to the two exploratory binary endpoints (clinical remission at Week 48, endoscopic response at Week 48). Unless otherwise specified, the ICEs are the same as those specified in Sections 5.4.2.1.

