6.2. Appendix 2 Prohibited Changes in CD Medications (Intercurrent Event 2)

(1) **Prohibited medications**

Initiation of the following prohibited medications after Week 0

- a. Immunomodulatory agents other than AZA, 6-MP, or MTX (including, but not limited to, 6-thioguanine, cyclosporine, mycophenolate mofetil, tacrolimus, and sirolimus).
- Immunomodulatory biologic agents (including, but not limited to, TNFα antagonists, natalizumab, ustekinumab, rituximab, vedolizumab).
- c. Experimental Crohn's disease medications (including, but not limited to, upadacitinib, filgotinib, ozanimod, etrolizumab, brazikumab, mirikizumab, risankizumab, and andecaliximab).
- d. Thalidomide or related agents.

(2) Corticosteroids

The occurrence of the following changes in corticosteroid usage during induction treatment (ie, before week 12), OR, between week 36 and week 48, including changes initiated before week 36 and continued after week 36, unless otherwise specified.

- a. Initiation of oral corticosteroids (including budesonide and beclomethasone dipropionate), parenteral, or rectal corticosteroids due to worsening Crohn's disease.
- b. Increase in the dose of oral corticosteroids (including budesonide and beclomethasone dipropionate), as specified below, above the baseline dose due to worsening Crohn's disease.
 - i. Oral corticosteroids > 5 mg/day (prednisone equivalent)
 - ii. Oral budesonide > 3 mg/day
 - iii. Oral beclomethasone dipropionate > 5 mg/day
- c. Initiation of oral corticosteroids (including budesonide and beclomethasone dipropionate) due to reasons other than worsening Crohn's disease for more than 7 days during induction treatment, OR, for more than 28 days during maintenance treatment.
- d. Increase in the dose of oral corticosteroids (including budesonide and beclomethasone dipropionate), as specified below, above the baseline dose due to reasons other than worsening Crohn's disease for more than 7 days during induction treatment, OR, for more than 28 days during maintenance treatment.
 - i. Oral corticosteroids > 5 mg/day (prednisone equivalent)
 - ii. Oral budesonide > 3 mg/day
 - iii. Oral beclomethasone dipropionate > 5 mg/day

(3) Immunomodulator agents

- a. Initiation of oral 6-MP/AZA due to worsening Crohn's disease.
- b. Initiation of oral, subcutaneous, or intramuscular MTX due to worsening Crohn's disease.
- c. Increase in the dose of oral 6-MP/AZA above the baseline dose due to worsening Crohn's disease.

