- d. Increase in the dose of oral, subcutaneous, or intramuscular MTX above the baseline dose due to worsening Crohn's disease (within the same route).

CONFIDENTIAL – FOIA Exemptions Apply in U.S.

(4) **5-ASA**

Initiation or increase of oral 5-ASA compounds due to worsening of Crohn's disease.

(5) Antibiotics

Initiation or change of antibiotics due to worsening Crohn's disease.

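### After Week 48, ICE 2 counts permitted immunomodulator, 5-ASA and antibiotic changes for worsening disease as failure but not corticosteroid changes, so exploratory Week 96 results depend on which drug was chosen

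*Protocol*

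**What the plan says.** **What is allowed.** Protocol 6.8.1 says that, after Week 48, 5-ASAs, corticosteroids, antibiotics, AZA/6-MP/MTX and nutritional therapy "may be administered and changed at the discretion of the investigator". SAP 1.2 gives the same permission: "After Week 48 and through Week 96, concomitant therapies for Crohn's disease including 5-ASAs, corticosteroids, antibiotics, and immunomodulators" are among the treatments that may be started or altered.

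**What is counted.** ICE 2 in SAP 5.4.2.1 is handled by the composite strategy, and its content is set by SAP Appendix 2:

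- Item (1), prohibited agents, applies from Week 0 with no end.
- Item (2), corticosteroids, applies before Week 12 or "between week 36 and week 48, including changes initiated before week 36 and continued after week 36, unless otherwise specified".
- Item (3), immunomodulators, for example "Initiation of oral 6-MP/AZA due to worsening Crohn's disease", gives no start or end week.
- Item (4), "Initiation or increase of oral 5-ASA compounds due to worsening of" Crohn's disease, gives no start or end week.
- Item (5), start or change of antibiotics for worsening disease, gives no start or end week.

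**Which events apply later.** SAP 5.5.3, in its part on analyses after Week 24, says: "Unless otherwise specified, the ICEs are the same as those specified in Sections 5.4.2.1". No different set is given for Week 96. For continuous endpoints, 5.5.3 sets scores back to baseline from a composite event on. SAP 5.7.4 treats ICE categories 1 to 3 and 5 as unfavorable in exposure-response analyses that include Week 96.

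**The concern.** Two participants flare at Week 60 and both receive a treatment that the protocol allows. Whether the Week 96 analysis calls them failures depends on the drug class that the investigator picked. Sites are unblinded after the Week 48 database lock, so that choice is made with the assignment known.

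The results at stake are Week 96 endoscopic response, remission and healing (SAP 5.5.2.5), Week 96 histology (5.5.2.10), the CDAI and PRO-2 endpoints followed over time (5.5.2.1 and 5.5.2.3), and exposure-response at Week 96 (5.7.4). Corticosteroid-free clinical remission is listed only for Weeks 24 and 48 (5.5.2.2), so no listed remission endpoint offsets the uncounted steroid use at Week 96.

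**Working it through.** The plan states no figure on this point, so there is none to reproduce. The check sets the rules side by side for one case: a change first made at Week 60 because of worsening Crohn's disease.

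| Change at Week 60 | Allowed by Protocol 6.8.1 and SAP 1.2? | Within Appendix 2? | Week 96 binary endpoint | Continuous score |
|---|---|---|---|---|
| Start or raise AZA/6-MP/MTX | Yes | Yes, item (3), no end week | Failure | Reset to baseline |
| Start or raise oral 5-ASA | Yes | Yes, item (4), no end week | Failure | Reset to baseline |
| Start or change antibiotics | Yes | Yes, item (5), no end week | Failure | Reset to baseline |
| Start or raise corticosteroids | Yes | No, item (2) ends at Week 48 | As observed | As observed |
| Start an item (1) agent | No (Protocol 6.8.2) | Yes, item (1) | Failure | Reset to baseline |

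The last row is consistent: those agents are prohibited throughout and counted throughout. The first four rows are not consistent with one another.

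Two details limit the finding. Items (3) to (5) count only changes made for worsening disease, so other permitted changes in those classes are not events. In item (2), the sub-items on steroid use for other reasons mention more than 28 days during maintenance. If that is read as otherwise specified, such use might count after Week 48, but steroids given for worsening disease still would not. Nutritional therapy, also permitted after Week 48, is not in Appendix 2 at all.

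**Size, as an illustration.** Let u be the share of an arm with a counted change after Week 48 and no earlier composite event, and r the share of those with an observed Week 96 response. Neither is in the documents; both are assumptions. Counting the change rather than ignoring it lowers the arm's responder rate by u × r, or 106 × u × r participants at the planned arm size of 106.

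| u | Points, r = 25% to 75% | Participants of 106 |
|---|---|---|
| 2% | 0.5 to 1.5 | 0.5 to 1.6 |
| 5% | 1.25 to 3.75 | 1.3 to 4.0 |
| 10% | 2.5 to 7.5 | 2.7 to 8.0 |
| 20% | 5 to 15 | 5.3 to 15.9 |

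Example: 10% × 50% = 5 points, and 106 × 0.10 × 0.50 = 5.3 participants. The same flares treated with corticosteroids shift the rate by 0. Between the two regimens, only the difference in u × r matters: with r = 50% in both, u = 10% in one and 5% in the other, the contrast moves by 5.0 − 2.5 = 2.5 points.

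**The case against.** The strongest reply is that Appendix 2 was meant for Weeks 0 to 48. Protocol 6.8.1 defers the analysis rules to the SAP inside its Week 0 to 48 part, SAP 1.2 points to Appendix 2 directly after the Week 0 to 48 restrictions, and the ICE label speaks of a prohibited change, which these no longer are. Also, the sentence in 5.5.3 just before the carry-over names only the two Week 48 endpoints. This is plausible as intent. But neither Appendix 2 nor 5.5.3 states it, the corticosteroid item shows that Appendix 2 writes a window where one is wanted, and 5.7.4 applies ICE 2 to Week 96 explicitly. A programmer following the text would count the change.

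Second, a permitted change can legitimately be a failure. Before Week 48, starting these drugs for medical necessity is not a protocol deviation, yet Appendix 2 counts it. That stands, so a reader should not infer that permission alone makes the rule wrong. What lacks a stated reason is applying it to three classes and not the fourth.

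Third, class-specific windows already exist: steroid changes from Week 12 to Week 36 are also uncounted. That gap starts with the mandatory taper, during which Protocol 6.8.1.1 allows temporary increases. This stands, and it is why one common window for items (2) to (5) at all times would be the wrong remedy.

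A reader might also infer that Week 96 benefit is understated. The documents do not support that as a general statement: under a composite estimand, need for added therapy is part of the outcome, so the direction depends on the estimand chosen.

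**Conclusion.** The point holds as an inconsistency in the written ICE 2 rule for analyses after Week 48, and it should be corrected before the Week 96 analysis.

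It is confined to exploratory results with nominal p-values. A reader might infer that the confirmatory results are at risk. They are not: the composite rule looks at events before the visit analyzed, so a change first made after Week 48 cannot alter a Week 12, 24 or 48 outcome. Nor is a maintained placebo comparison affected, because placebo participants who were not rescued stop at unblinding and meeting the rescue criteria is already a composite failure. What can move is the long-term guselkumab rates, the comparison of the two regimens, and Week 96 exposure-response.

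The size is unknown. The illustration spans 0.5 to 15 points per arm over assumed usage of 2% to 20% and assumed response of 25% to 75%. The unequal treatment of drug classes does not depend on those assumptions.

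**What to change.** Leave Appendix 2 as it is for every analysis through Week 48, including the Week 12 to 36 steroid gap, so that the Week 24 secondary and controlled Week 48 tests do not change. Add to SAP 5.5.3 and Appendix 2 a rule only for changes first made after Week 48 that treats corticosteroids, immunomodulators, 5-ASA and antibiotics alike. The default that matches Protocol 6.8.1 and SAP 1.2 is to limit items (3) to (5) to changes through Week 48, with item (1) continuing throughout. Say in 5.7.4 that the same rule applies there.

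The cost is SAP wording and a date condition in the ICE 2 derivation; no new data are needed. Because full sponsor unblinding occurs at the Week 48 lock, the choice should be dated and documented before the Week 96 lock. The small downside is that Week 96 results would then include participants who received permitted added therapy, which the table footnotes should say.

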6.8.1.1. Oral Corticosteroids Tapering

At Week 12, all participants who were taking corticosteroids at Week 0 must begin tapering corticosteroids. This tapering is mandatory, unless not medically feasible, and should follow the recommended schedule shown in Table 6. If participants experience worsening of their disease activity while tapering corticosteroids, further dose decreases may be suspended, and/or their oral corticosteroid dose may be temporarily increased if deemed necessary by the investigator. The oral corticosteroid dose, however, may not be increased above the Week 0 dose unless due to medical

necessity. For participants whose corticosteroid taper is interrupted, investigators are encouraged to resume tapering within 4 weeks. Tapering may exceed this schedule only if warranted by medical necessity (eg, participant experiencing corticosteroid-related side effects).

Table 6: Recommended Tapering Schedule for Oral Corticosteroids

Recommended Tapering Schedule for Oral Corticosteroids (Other Than Budesonide)				
Dose >15 mg/day prednisone or equivalent	Taper daily dose by 5 mg/week until receiving			
	10 mg/day, then continue tapering at 2.5 mg/week until			
	0 mg/day			
Dose 11 to 15 mg/day prednisone or	Taper daily dose to 10 mg/day for 1 week, then continue			
equivalent	at 2.5 mg/week until 0 mg/day			
Dose ≤10 mg/day prednisone or equivalent	Taper daily dose by 2.5 mg/week until 0 mg/day			
Recommended Tapering Schedule for Oral Budesonide				
Participants receiving budesonide should have their daily dose tapered by 3 mg every 3 weeks until				
0 mg/day.				

6.8.2. Prohibited Concomitant Medications

Participants who initiate the following treatments during study participation will have their study intervention discontinued:

- Immunomodulatory agents other than AZA, 6-MP, or MTX (including, but not limited to 6-thioguanine, cyclosporine, mycophenolate mofetil, tacrolimus, and sirolimus)
- Immunomodulatory biologic agents (including, but not limited to, TNFα antagonists, natalizumab, ustekinumab, rituximab, vedolizumab)
- Experimental Crohn's disease medications (including, but not limited to upadacitinib, filgotinib, etrasimod, ozanimod, etrolizumab, brazikumab, mirikizumab, risankizumab, and andecaliximab)
- Thalidomide or related agents

The sponsor or designee must be notified in advance (or as soon as possible thereafter) of any instances in which prohibited therapies are administered.

As protection of human research participants is paramount, it is recognized that initiating such therapies may rarely be required due to medical necessity. However, initiation of these prohibited medications should be documented as a deviation from the study protocol, and participants will be discontinued from receiving further study intervention. Participants who discontinue study intervention administration should complete a SID visit and an FES follow-up visit as described in Section 1.3.

Note: Participants must not receive guselkumab outside of the protocol or participate in any other clinical study with an investigational agent while in this study and must terminate study participation if they do. Prior to termination of study participation, participants should complete evaluations for a SID visit as described in Section 1.3.

6.8.3. Vaccinations (Including COVID-19)

When considering use of locally-approved (including emergency use-authorized) COVID-19 vaccines in study participants, consider protocol lifestyle considerations (Section 5.3) and follow applicable local vaccine labeling, guidelines, and standards of care for patients receiving immune-targeted therapy.

For study participants receiving a locally-approved (including emergency use-authorized) COVID-19 vaccine, in order to help identify acute reactions potentially related to the COVID-19 vaccine, it is recommended that, where possible, vaccine and study intervention be administered on different days, separated by as large an interval as is practical within the protocol.

Participants must not receive live viral, live bacterial, or BCG vaccinations during the study and for 12 weeks after receiving the last dose of study intervention (Section 5.3).

7. DISCONTINUATION OF STUDY INTERVENTION AND PARTICIPANT DISCONTINUATION/WITHDRAWAL

If a participant discontinues study intervention or withdraws from the study before the end of the study, assessments should be obtained as specified in the SoA (Section 1.3).

7.1. Discontinuation of Study Intervention

A participant who discontinues study intervention will not be automatically withdrawn from the study (see Section 7.2).

A participant's study intervention must be discontinued if:

- 1. The participant initiates treatment with prohibited therapies for Crohn's disease (Section 6.8).
- 2. The participant has a Crohn's disease-related surgery that represents a lack of efficacy of study intervention or that will preclude the future ability to assess efficacy using the CDAI or other instruments required for demonstration of efficacy endpoints.
 - Note: Other permitted Crohn's disease-related surgeries (eg, to resolve long-standing complications such as strictures or for symptomatic nonhealing fistulas, in participants experiencing improvement on study intervention) other than minor procedures (eg, placement of a seton or cutaneous drainage of an abscess) should be postponed until after the FES follow-up visit, unless necessary to ensure participant well-being and/or safety.
- 3. The participant becomes pregnant or plans a pregnancy within the study period (Section 8.3.5).
- 4. The participant (or the participant's representative) withdraws consent to receive study intervention.
- 5. The participant develops a systemic opportunistic infection.
- 6. The participant meets **ANY** of the following TB-related conditions:
 - A diagnosis of active TB is made.

- A participant has symptoms suggestive of active TB based on follow-up assessment questions and/or physical examination or has had recent close contact with a person with active TB and cannot or will not continue to undergo additional evaluation.
- A participant undergoing evaluation has a chest imaging with evidence of current active TB and/or a positive IGRA test result, unless active TB can be ruled out and appropriate treatment for latent TB can be initiated prior to the next administration of study intervention and continued to completion (see also Section 8.2.10). Indeterminate/borderline results should be handled as outlined in Section 8.2.10.
- A participant receiving treatment for latent TB discontinues this treatment prematurely or is noncompliant with the therapy.
- 7. The participant has a serious adverse reaction that is related to an injection, including an injection-site reaction, resulting in bronchospasm with wheezing and/or dyspnea that requires ventilatory support **OR** that results in symptomatic hypotension with a decrease in systolic blood pressure >40 mmHg or blood pressure <90/60 mmHg.
- 8. The participant has a reaction resulting in myalgia and/or arthralgia with fever and/or rash (suggestive of serum sickness and not representative of signs and symptoms of other recognized clinical syndromes) occurring 1 to 14 days after an injection of study intervention. These may be accompanied by other events including pruritus, facial, hand, or lip edema, dysphagia, urticaria, sore throat, and/or headache.
- 9. The participant has a malignancy including squamous cell skin cancer. Consideration may be given to allowing participants who develop ≤2 basal cell skin cancers that are adequately treated with no evidence of residual disease to continue to receive study intervention.
- 10. The participant has severe liver test abnormalities that are not transient and are not explained by other etiologies, as described in Section 8.2.4 and Appendix 9 (Section 10.9).
- 11. The investigator believes that for safety reasons or tolerability reasons (eg, AE), it is in the best interest of the participant to discontinue study intervention.

Discontinuation of a participant's study intervention must be strongly considered under the following conditions:

- 12. Persistent inadequate response or worsening of Crohn's disease:
 - a. The participant has a CDAI score >220 and <70-point reduction from baseline CDAI at both Week 20 and Week 24.

OR

b. The participant experiences AEs consistent with clinically significant worsening of Crohn's disease at any time during the study.

These events must be evaluated by the investigator. A consultation with the study medical monitor may also be considered, at the investigator's discretion. Discontinuation of study intervention must be considered in participants with clinically significant worsening of Crohn's disease where continuation of the study intervention is not in the best interest of the participant.

13. The participant develops a serious infection, including but not limited to sepsis or pneumonia.

- 14. The participant reports suicidal ideation with intention to act ("Ideation level 4"), suicidal ideation with specific plan and intent ("Ideation level 5"), or any suicidal behavior (actual suicide attempt, interrupted suicide attempt, aborted suicide attempt, or preparatory behaviors for making a suicide attempt) on a post-baseline C-SSRS assessment. If a participant can be adequately treated with psychotherapy and/or pharmacotherapy based on an evaluation by a mental health professional, then the participant, at the discretion of the investigator, may be continued with treatment if agreed to by the medical monitor or designee. Discussion of such participants with the medical monitor or designee is required.
- 15. The participant develops a severe injection-site reaction.

If a participant discontinues study intervention for any reason before the end of the treatment period, then the assessments as specified in the SoA (Section 1.3) should be obtained. If the reason for discontinuation of study intervention is withdrawal of consent, every effort should be made to conduct the SID visit assessments, as indicated in the SoA, prior to terminating study participation. After termination of study participation, no additional assessments are allowed. Study intervention assigned to the participant who discontinued study intervention may not be assigned to another participant. Additional participants will not be entered.

